7.3.1.2 Overall survival

• Overall survival is defined as time from diagnosis to death from any cause. i.e.Death information:- date and major cause (if applicable).

7.3.1.3 Hematological remission status

• Standard hematology panel, including required laboratory parameters to define complete hematological remission. Parameters for complete hematological remission defined in Section 7.4.2.4.

7.3.1.4 Minimal residual disease (MRD) response

• MRD response assessed via the detection of BCR-ABL transcript, collected at specified time-points. Time-points defined fully in Section 7.4.2.5. MRD response is defined as any negative level of MRD, i.e. MRD <0.01%.

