6 Research question and objectives

The main objective is to collect data to describe long-term clinical outcomes measured by event-free survival (EFS), overall survival (OS) and long-term safety in newly diagnosed Ph+ ALL pediatric patients treated with imatinib in combination with chemotherapy

This multi-center, registry is not designed to test a formal hypothesis, but has been initiated as part of the post-marketing commitment to the type II variation EMEA/H/C/000406/II/80, in order to address the limitations related to the limited size of the efficacy and safety database (up to 92 patients evaluated for efficacy and 220 patients evaluated for safety in prospective studies).

Objectives and related main variables under study are described in Table 6-1 below.

Confidential

Table 6-1 Objectives and related main variables

Objective	Main Variables	Analysis
Primary		Refer to Section 7.7
To evaluate long term clinical outcome measured by event-free survival (EFS, events defined as: relapse, death , secondary malignancies)	EFS, defined as time from diagnosis to relapse at any site, development of a second malignant neoplasm or death.	
Main secondary		
To evaluate overall survival	OS, defined as time from diagnosis to death from any cause.	
To evaluate safety	Adverse events and serious adverse events in the observation period.	
Other secondary		
To evaluate hematological remission status	Hematological remission status. Complete hematological remission requires that all of the following are present: a) Adequate bone marrow cellularity with a blast count < 5%, b) No peripheral blood blasts, c) ANC ≥1500/µl, d) Platelet count ≥100.000/µl, e) No evidence of extramedullary involvement	
To evaluate minimal residual disease (MRD) response	MRD response evaluated via detection of BCR-ABL transcript (e.g. determined via quantitative real-time PCR of mononuclear bone marrow and peripheral blood cells or detection by flow cytometry).	
To evaluate duration of complete remission	Complete remission and duration of complete remission (CR, defined as <5% blasts in bone marrow aspirate regardless of proportion of mature lymphocytes).	
To evaluate time to transplantation, time to engraftment, engraftment failure, graft versus host disease	Transplant and time to transplant from diagnosis. Time to engraftment and engraftment failure Incidence of graft versus host disease (acute and chronic)	

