7.4.2.5 Molecular response

MRD assessments to detect BCR-ABL transcript will be evaluated at specific time-points (if available) to provide a measure of the molecular response. Biondi et al. 2012 define the 5 time-points as the following: post-frontline induction; pre-consolidation block 1, pre-consolidation block 2, pre-consolidation block 3, post-consolidation.

MRD assessments may be performed for example via quantitative real-time PCR of mononuclear bone marrow and peripheral blood cells or detection by flow cytometry. Data should be provided if available at the aforementioned time-points.

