7.7 Data analysis

All analyses will be performed by a Novartis representative and/or designee.

All data summaries and analyses will have descriptive purposes only with no formal inferential testing.

Due to the observational nature of this registry, it is expected that some specific endpoints may not be available at all time points and for the entire population. Unless otherwise specified in the Reporting Analysis Plan, the analyses will be performed on available data.

Patient efficacy, safety and tolerability outcomes of patients treated with chemotherapy + imatinib will be summarized overall, by HSCT (yes/no) and by risk group (good-risk/induction-responder) / (poor-risk/induction non-responder).

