7.7.4.3 Other secondary endpoints

The other secondary efficacy analyses will be the evaluation of the following outcomes:

- 1. Rate of Complete Remission (CR) CR is defined in Section 7.3.
- 2. Duration of first complete remission This is defined as the time between date of first complete remission to the date of loss of first complete remission.
- Rate of Complete Hematological Remission CHR response (Complete Hematological Remission) is defined in Section 7.3.
- 4. Rate of MRD response MRD response (Minimal residual Disease) is defined in Section 7.3.
- 5. Time to first transplantation This is defined as the time from date of diagnosis to the date of first transplantation.
- 6. Time to engraftment (neutrophil, platelet and both neutrophil/platelet) This is defined as the time from date of transplant to the date of engraftment.
- 7. Rate of engraftment failure
- 8. Rate of acute Graft versus Host disease
- 9. Rate of chronic Graft versus Host disease

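### MRD response equates a negative result with MRD below 0.01%, sets no assay sensitivity, and names an analyte that one accepted method does not measure

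*Protocol*

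**What the plan says.** Section 7.3.1.4 fixes two things. The analyte: "MRD response assessed via the detection of BCR-ABL transcript, collected at specified time-points". The responder rule: "MRD response is defined as any negative level of MRD, i.e. MRD <0.01", the figure being a percentage.

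Table 6-1 (Section 6) names the same analyte, "MRD response evaluated via detection of BCR-ABL transcript", and then gives PCR of marrow and blood cells, or flow cytometry, as examples of how it is determined. Section 7.4.2.5 repeats the list: "MRD assessments may be performed for example via quantitative real-time PCR of mononuclear bone marrow and peripheral blood cells or detection by flow cytometry". It names five time-points, "post-frontline induction; pre-consolidation block 1, pre-consolidation block 2, pre-consolidation block 3, post-consolidation", with data to be given if available.

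Section 7.7.4.3 lists the endpoint once and sends the reader back: "Rate of MRD response MRD response (Minimal residual Disease) is defined in Section 7.3". Under Section 7.7, outcomes "will be summarized overall, by HSCT (yes/no) and by risk group". Section 7.7.4.4 attaches exact (Clopper-Pearson) 95% intervals to rates and plans to explore MRD against OS and EFS. Its subgroups for OS and EFS are age, lymphoblast count, trial enrolment and donor type.

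Section 7.4.1 says that the registry imposes no diagnostic procedure, so the test used is the local one. The protocol sets no minimum assay sensitivity, does not say which sample counts, and does not say how to class a negative from an assay that cannot reach 0.01%.

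**The concern.** A negative result means that nothing was found above that assay's detection limit. A result below 0.01% is a statement about the amount of disease. Joining the two as equivalent works only when the detection limit is 0.01%, and nothing in the protocol requires that.

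The accepted methods also do not match the named analyte. Flow cytometry identifies cells by their markers and does not detect a transcript, so a flow result falls outside the definition as worded while the same protocol invites it.

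At stake are the MRD response rate, its confidence interval, its split by HSCT and risk group, and the exploration of MRD against EFS and OS. Each could partly reflect which test a site happened to use. The confidence interval would not show this, because it covers sampling error only.

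**Working it through.** The protocol gives no expected MRD rate, no MRD distribution and no sample size calculation, so there is no figure of its own to reproduce. The first step needs only the text. The others are illustrations on stated assumptions.

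**1. The two clauses side by side.**

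| True MRD | Assay detection limit | Read-out | By the negativity clause | By the 0.01% clause |
|---|---|---|---|---|
| 0.05% | 0.1% | negative | responder | not a responder |
| 0.005% | 0.001% | positive | not a responder | responder |
| 0.005% | 0.01% | negative | responder | responder |

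The clauses disagree in both directions once the limit moves away from 0.01%.

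**2. What a negative can rule out.** Suppose k cells or copies are examined and none is positive (a simple counting model, an assumption).

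The chance of a negative at true level m is (1 − m)^k. For m = 0.05%, five times the cut-off:
- k = 1,000: 0.9995^1,000 = 61%
- k = 3,000: 22%
- k = 10,000: 0.7%

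The upper 95% bound on MRD after no hits is 1 − 0.05^(1/k):
- k = 1,000: 0.30%
- k = 10,000: 0.030%
- k = 30,000: 0.010%

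Under this model a negative supports MRD below 0.01% only when about 30,000 cells or copies were examined.

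**3. Effect of less sensitive tests on the rate.** Let p be the true response rate, s the share of children with a less sensitive test, and f the share of true non-responders that this test reads as negative. If every negative counts as a response, the apparent rate is p + (1 − p) × s × f. With f from 10% to 50%:
- p = 60%, s = 25%: 0.60 + 0.40 × 0.25 × f = 61% to 65%
- p = 60%, s = 50%: 0.60 + 0.40 × 0.50 × f = 62% to 70%
- p = 60%, s = 100%: 0.60 + 0.40 × f = 64% to 80%
- p = 40%, s = 50%: 0.40 + 0.60 × 0.50 × f = 43% to 55%

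**4. Effect of more sensitive tests.** Let a share t of children have an assay that reaches below 0.01%, and let it read a share g of true responders as positive. If every positive counts as non-response, the apparent rate is p × (1 − t × g). With p = 60%, t = 50% and g from 10% to 50%, it is 0.60 × (1 − 0.05) = 57% down to 0.60 × (1 − 0.25) = 45%. The bias now runs downwards.

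**5. The extreme case.** Assume log10 MRD is normal with median 0.01% to 0.1% and SD 1.0 to 1.5 logs. The share truly below 0.01% is 16% to 50%. If every child were tested at a 0.1% limit and every negative counted, the share would be 50% to 84%, a gain of 25 to 38 points. If every child were tested at a 0.001% limit and only negatives counted, it would be 2% to 25%.

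**6. Scale.** At the planned minimum of 50 patients, 30 responders give an exact 95% interval of 45.2% to 73.6%.

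**The case against.** The strongest reply is that the abbreviation joining the two clauses makes 0.01% the meaning of negative. On that reading a negative from a 0.1% assay shows nothing about 0.01% and does not qualify, and a PCR value of 0.005% does. The reading is available, so the most that can be said is that an insensitive assay can make a child a responder, not that it does. But the text never says that the threshold governs, and a site or programmer who takes the word negative from a laboratory report is also following it.

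A second reply is that rows by assay and rules for non-evaluable results belong in the analysis plan, which is not shown. That holds for the layout of tables, and a missing split is not the fault here. A reader might infer that all results will be pooled into one figure. The document lists one rate and names no split by assay or sample, but it gives no instruction to pool and does name five time-points. The responder rule is different: it stands in the protocol, and a plan that follows it inherits the ambiguity.

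A reader might also infer that blood samples inflate the rate because blood reads lower than marrow. The protocol says nothing of the kind, nor does it call the two interchangeable. It accepts both without saying which counts.

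A reader might infer a sizeable upward bias from the 25 to 38 points. That needs every child to be tested at a 0.1% limit, and the document does not show that any site uses such an assay. Step 4 shows that the error can run the other way.

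Finally, a registry cannot impose an assay. That stands, and it rules out marrow-only or PCR-only restrictions as corrections: they would be design preferences. It does not prevent recording what was done. Section 7.4.2.2 already does this for risk group, where the definition used is to be obtained if it differs from the suggested one.

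**Conclusion.** The definition is faulty as written. It joins two rules that can class the same child in opposite ways, attaches no sensitivity condition, and names a transcript while accepting a method that does not detect one.

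The net direction and size of the resulting bias are unknown, because they depend on the mix of assays and samples. With an assumed true rate of 60%, half the children on a less sensitive test would move the rate to between 62% and 70%. Half on a more sensitive test, under the negativity clause, would move it to between 45% and 57%. Both ranges assume that 10% to 50% of the relevant children are misread. Several of these shifts are small beside sampling error at 50 patients, but a larger registry would not reduce them.

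The reach is limited: one of nine other-secondary outcomes in a descriptive study, plus an exploratory association. The definition of EFS and OS, and their analysis, are unaffected. The point deserves correction before analysis but does not threaten the study's main result.

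**What to change.** In Section 7.3.1.4, delete the clause on any negative level and define MRD response as MRD below 0.01% by an assay whose detection limit for that sample is 0.01% or lower. Class a negative with a worse or unknown limit as not evaluable. Reconcile the analyte wording in Sections 6 (Table 6-1), 7.3.1.4 and 7.4.2.5 with flow cytometry, either by widening the definition to MRD by a stated method or by reporting flow results under their own label.

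Record assay type, sample type and detection limit with each MRD result where available. Table 7-1 already makes MRD a database item; the eCRF is not shown, so some of these fields may exist. Show the response rate and the MRD exploration against EFS and OS by assay and sample type, in the protocol or the analysis plan. None of this imposes a test on any site.

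The cost is fewer evaluable patients for this endpoint and some retrospective retrieval of laboratory details. At Amendment 2, 41 patients were already enrolled against a minimum of 50, and eligible trial entries reach back to January 2012.

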7.3.1.5 Complete remission

- Complete remission is defined as < 5% blasts in bone marrow aspirate regardless of proportion of mature lymphocytes.
- The duration of complete remission is defined as the time from the date of first complete remission to the date of loss of complete remission (Section 7.4.2.4).

7.3.1.6 Time to transplant, time to engraftment, engraftment failure, graft versus host disease

- Time to transplant is defined from the date of diagnosis until the date of the transplant procedure.
- Time to engraftment (neutrophil, platelet and both neutrophil/platelet engraftment) is defined as the time from the date of transplant to the date of engraftment.
- Engraftment failure is defined as either definitive engraftment failure or the absence of engraftment.
- Presence/ absence of graft versus host disease; chronic or acute (Section 7.4.2.6).

7.3.1.7 Assessment of growth and development

• Physical examination information, including the standard growth & development measures of height and weight, and sexual maturity (Section 7.4.2.7, Section 7.4.2.9 and Section 7.4.2.10).

7.3.1.8 Safety

• Adverse events (including serious adverse events) from start of imatinib (Glivec[®]) treatment.

Solicited safety information including serious adverse event reports, if any, will be handled through the Chief Medical Office and Patient Safety (CMO&PS) drug safety surveillance process (Section 9).

An adverse event is defined as the appearance of (or worsening of any pre-existing) undesirable sign(s), symptom(s), or medical condition(s) that occur after a patient starts imatinib treatment.

All adverse events are to be collected and recorded for this registry regardless of relatedness (suspected or non-suspected). In order to comply with the 2012 EMA legislation on adverse event reporting in non-interventional trials, adverse events that are suspected to be related to

imatinib (Glivec[®]) are required to be reported to competent health authorities. Adverse events identified as part of this registry will be included in the annual study progress reports to the EMA.

In the context of this registry, adverse events will be collected in the clinical database (eCRF) from the date of start of imatinib (Glivec[®]) treatment. For further details on AE collection and reporting, including laboratory abnormalities, refer to Section 9. Accurate reporting of SAEs occurring during this period will be verified in accordance with the Site Monitoring Plan (Section 7.8.3).

• Information on all AEs is included in the individual patient eCRFs which must be updated in the registry database on a periodic basis, but not later than one month of new information becoming available.

For the duration of the registry, SAE reporting should continue via normal procedures, through the local Novartis CMO&PS office, as detailed in Section 9. Reporting and follow-up is independent of participation in the registry, although reconciliation will occur.

7.3.1.9 Drug Exposure

An assessment of imatinib (Glivec[®]) exposure will be calculated using the duration of treatment (date of first dose of imatinib until the last dose of imatinib), captured within the dose administration record (Section 7.4.2.11). The concomitant antineoplastic therapy (chemotherapy) regimen will be recorded on the Antineoplastic therapy – Medications CRF.

7.4 Data sources

The data for this registry will be retrieved from hospital discharge files, clinical records and electronic medical records (e.g. laboratory reports of baseline assessment data etc.).

Initiation of the participating sites will be performed by a Novartis representative and/ or designee. Before registry initiation, a Novartis representative and/ or designee will review the protocol and eCRF with the treating physicians and their staff.

Sites enrolling patients in this registry will record data on eCRFs designed by a Novartis representative and/ or designee. The database will capture, perform standard edit checks and store the data.

Concomitant or prior medications entered into the database will be coded using the World Health Organization (WHO) Drug Reference List. Relevant medical history/ current medical conditions and adverse events will be coded using the Medical dictionary for regulatory activities (MedDRA) terminology.

Safety data will be transferred to Novartis on a monthly basis as defined in Section 9 of this protocol. Clinical data will be transferred to Novartis on once yearly (minimum).

7.4.1 Data collection schedule

This is a non-interventional registry and does not impose a therapy protocol, diagnostic/ therapeutic procedure, or a visit schedule. Patients will be treated according to the local prescribing information, and routine medical practice in terms of visit frequency and the types of assessments performed for disease evaluation, and only these data will be collected as part of the registry. The treating physician and/ or designee are asked to complete the appropriate electronic Case Report Form (eCRF) at every patient visit, where possible. For each patient enrolled in the registry a minimum of a once yearly update (12 ± 2 month intervals) of data in the registry database must occur to ensure an ongoing data stream, with the exception of safety data which should be entered within a month of new information becoming available. Where disease evaluation is performed frequently, any follow-up information collected that is relevant to the objectives of this registry should be recorded in the database. Long term safety and efficacy data will be collected such that the observational follow-up for each patient will be a minimum of 5 years from start of imatinib treatment or such available data until early patient discontinuation (Section 7.2.5).

Table 7-1 is a data collection schedule that outlines all the assessment information required by the registry and indicates with an "X", the visits when they are recorded. All data obtained from these assessments must be supported in the patient's source documentation. The table indicates which assessments produce data to be entered into the clinical database (D) or remain in source documents only (S) ("Category" column). The expectation is that laboratory assessments/ interventions shown are those required for the standard disease management of pediatric Ph+ ALL, according to local best practice.

• Where complete laboratory assessments/ interventions are not performed, it will be acceptable to indicate not done.

For each patient discontinuation, the reason for discontinuation should be determined.

Novartis Non-interventional study protocol – v02 (Clean)

Confidential

Table 7-1Data collection schedule

			Surve		Surveillance	urveillance Period			
	tegory	Protocol	reening rollment	agnosis Iseline	On Treatment Follow-Up	End of study Treatment (EOT)	Post- Treatment Follow-Up	Study Evaluation Completion	Survival follow-up
	ပီ	Section	ыs	Ba	Visit Dates	EOT Date	Visit Dates	EOS Date	SURV Visit
Follow-up Visit			1	2	601	777	602	778	888
Obtain Informed Consent	D	8	Х						
Patient history				-					
Inclusion/ exclusion criteria	D	7.2.2	Х						
Demography	D	7.4.2.1	Х						
Relevant medical history / current medical conditions	D			х					
Prior / Concomitant medications	D			х	Х	x			
Concomitant antineoplastic therapy	D			Х	Х	Х			
History and diagnosis of disease	D			Х					
Induction Response [Poor / Good]	D	7.4.2.2		х					
Physical examination									
General Physical Examination	S	7.4.2.7		Х	Х	Х	Х	Х	
Performance status	D	7.4.2.8		Х	Х	Х	Х	Х	
Vital Signs [Height / Weight]	D	7.4.2.9		Х	Х	Х	Х	Х	
Development & Growth [Tanner Staging]	D	7.4.2.10		х	Х	x	x	X	
Laboratory assessments	•		•	•				-	
Response status [Efficacy]	D	7.4.2.3		Х	X	X	Х	X	

Novartis Non-interventional study protocol – v02 (Clean)

Confidential

Page 25 STI571 / Glivec[®] / CSTI571I2201

			مة	_	Surveillance	Period			
	ategory	Protocol	creening .	agnosis i aseline	On Treatment Follow-Up	End of study Treatment (EOT)	Post- Treatment Follow-Up	Study Evaluation Completion	Survival follow-up
	ů	Section	ы К	Di B	Visit Dates	EOT Date	Visit Dates	EOS Date	SURV Visit
Follow-up Visit			1	2	601	777	602	778	888
Hematology	D	7.4.2.4		Х	Х	Х	Х	Х	
BM assessment / cytogenetics	D			Х	Х	Х	Х	Х	
MRD assessment	D	7.4.2.5		Х	Х	Х	Х	Х	
Extramedullary involvement [Cerebro-spinal Fluid Exam]	D			х	х	х	Х	х	
Safety									
Adverse events / Serious adverse events	D	7.3.1.8		Х	Х	х	Х	Х	
Drug administration (imatinib dosing)	D	7.4.2.11		Х	Х				
Surgery									
Transplantation and engraftment [Hematopoietic Stem Cell Treatment (HSCT)]	D	7.4.2.6			X	X	X		
End of study treatment (EOT)	D					X			
Study Evaluation Completion	D							X	
Overall Survival	D	7.3.1.2							Х

7.4.2 Assessments

7.4.2.1 Patient demographics and other pre-treatment characteristics

- Demographic information and other background or relevant medical history (i.e. age at diagnosis, sex, race, extent of disease)
- Information relating to patient eligibility and inclusion criteria (i.e. date of diagnosis, date of obtained informed consent).
- Details of all relevant prior concomitant medications, post-diagnosis.
- Updated information and details of new concomitant medications and significant non-drug therapies.
- Concomitant antineoplastic therapy details (i.e. full chemotherapy regimen).

